1 INTRODUCTION

1.1 PROBLEM DEFINITION

The use of plastics in medical specialties, dentistry being no exception, has been a singular advance in the prevention of the spread of diseases. However, some of them contain substances considered endocrine disruptors that mimic or antagonise the action of endogenous hormones, alter their metabolism and synthesis, and modulate the levels of their receptors. Given their impact on health and well-being, the evolution in this respect has been remarkable: in 1993 Colborn et al. coined the concept "endocrine disruption"; Weybridge in 1996 defined endocrine disruptor (ED) as: "an exogenous substance or mixture that alters the functions of the endocrine system, causing adverse health effects in an intact organism, its progeny or (sub)populations". In 2002, the World Health Organisation (WHO) and the International Programme on Chemical Safety (IPCS) clarified what *can cause* such alterations (endocrine disrupting potential). In 1999, the European Commission published the communiqué: *Community strategy on endocrine disruptors, a series of substances suspected of interfering with the hormone systems of humans and wildlife*. On 1 June 2007, the REACH (Registration, Evaluation, Authorisation and Restriction of Chemicals) regulation comes into force to collect and evaluate information on the properties and hazards of substances. The European Chemicals Agency (ECHA) also considers substances of very high concern (SVHC). These are substances that may have serious and often irreversible effects on human health and the environment, and are listed in Annex XV of the REACH regulation. It is established at the level of

European a guideline to follow: Identify to assess and monitor. In 2019, the European Commission created a "roadmap" for the review of compliance with the "Fitness Check" for endocrine disruptors, which aims to protect health and the environment.

Numerous organisations, objectives, and laws are shaped. Among these provisions, those concerning dental devices or restorations are shown in section 10.4 of Annex 1 of the European Medical Devices Regulation (MDR) Regulation (EU) 2017/745, focusing on action on the identification of substances considered carcinogenic, mutagenic or toxic for reproduction (CMR) and/or endocrine disruptors.

In dentistry, the use of polymers, acrylics or resin-based composites (RBC) ranges from dental cements, fissure sealants, temporary acrylic materials, definitive and aesthetic restorations, partial dentures, to splints for the treatment of bruxism. Efforts are being made to develop materials that not only aesthetically but also biomechanically mimic the teeth and are easily repairable. This is why plastic materials are becoming increasingly popular in all dental specialties, from paediatric dentistry to gerontology. However, it is striking to find in their composition monomers such as bisphenol A (BPA), triethylene glycol dimethacrylate (TEGMA), methacrylate urethane, BisGMA copolymer (UDMA), or hydroxyethyl methacrylate (HEMA), substitutes for bisphenols: Bisphenol S (BPS), Bisphenol F (BPF), among others; whose purpose is to provide malleability, adhesion and strength, but which are not inert, by their nature. The possible hormonal, endocrine, neuronal, carcinogenic, mutagenic, etc. effects of the most common endocrine disruptors such as bisphenols and phthalates are well known, but even their substitutes have undesirable physiological effects. The effects of endocrine disruptors (EDs) and substances of particular concern (SVHCs) also alter dental genesis, as well as the microbiome, facilitating the proliferation of series with higher parodontogenic or cariogenic potential, favouring the two most common pathologies such as caries and periodontitis, and even malignant lesions and alterations in tooth formation (*Bisphenol A and Incisive Molar Hypomineralisation:: Topic Review - Dialnet*, n.d.; Chimenos-Küstner et al, 2019; Chimenos-Küstner & EM, n.d.; Da & Tavares, n.d.; Jacomossi, 2019; Piedrahita Sánchez et al., 2021; Tejada, 2021) .

Their dose-response curve is not monotonic, they alter biogenesis, being up to childbearing age, the window of greatest risk (Kakonyi et al., 2021). If we take into account that our activity reverts at any time in the life cycle of the population, the time that the restorations or devices remain in the mouth, the oral conditions (pH, occlusion, temperature...) that facilitate the wear and release of particles, and clinical protocols with levels of evidence that can be improved, it would be desirable to know the current status of dental materials of a plastic nature, in accordance with European regulations on identification and prevention (de Angelis et al., 2022; de Nys, D., 2022), 2022; de Nys, Duca, et al., 2021; Mulligan et al., 2022; van Landuyt et al., 2011; Vervliet et al., 2022).

1.2 BACKGROUND

Despite the fact that the dose-effect curve is not monotonic, in 2015 the European Food Safety Authority (EFSA) published a new global limit for BPA exposure and toxicity at 4 µg/kg body weight/day, compared to the 50 µg/kg/day estimated by the US Environmental Protection Agency (USEPA) in 1993 ("Hormones and Endocrine-Disrupting Chemicals: Low-Dose Effects and Nonmonotonic Dose Responses", published in March 2012 in Endocrine Reviews). On 15 December 2021, a draft proposal was made to reduce the limit by 0.04ng/kg/day, in view of the evidence shown in the literature from 2015-2018 ([publication and testing of the risk assessment protocol](#) in 2017 and EFSA <https://www.efsa.europa.eu/en> in 2019). With regard to BPA substitutes, it is observed that some show even more genotoxicity, such as BPF; alterations in testosterone levels such as bisphenol B (BPB); or obesogenic activity such as BPS ((Alharbi et al., 2022; Chen et al., 2023; Karrer et al., 2018; Lu et al., 2022; Moreno-Gómez-Toledano et al., 2022, vansecal II, Tolerable Dose Intake).

Despite all this, an alternative to plastic materials is not foreseen in the short to medium term, on the contrary: an increase of 6.9 to 13% of aligners is estimated in France, Italy and Germany (Koletsi et al., 2022), and the compound annual growth rate (CAGR) is estimated to be 13.5% between 2020 and 2025 (Mordor Intelligence, industries reports). This same upward trend extends to relaxation splints, made of acrylic materials, which remain in the mouth for at least 6h/day for years. These are part of the treatment of bruxism. The 'White Paper 2023: population-based survey of oral health in post-pandemic Spain 2023', shows an increase in the number of patients with bruxism.

increase from 6% in 2019, to 23% at present, in Spain ((Carrillo-Diaz et al., 2022; Dias et al., 2022; *List of Results: BRUXISM INCREASE AFTER COVID: EBSCOhost*, n.d.; Osses-Anguita et al., 2023). This is because its aetiology is closely associated with stress. One of the consequences of bruxism is the fracture of teeth, whether or not they are devitalised. As an alternative, the restoration of lost tooth tissue is indicated with inlays made of ceromers (among others). These materials fall into the group of dental composites (divided into reinforced, universal, flowable and other composites for everyday clinical use), whose global market was valued at US\$ 24.7 Mn in 2021. It is estimated to grow at a CAGR of 9.0% from 2021 to 2031, and by the end of 2031, the global dental composites market is expected to reach a value of US\$ 59.3 Mn. This trend extends to all fields of dentistry, due to its characteristics, as described above. The dental materials industry is also focusing on improvements in the manufacturing process of the devices (injection moulded, subtraction or milled, addition or horizontal/vertical impression) achieving a sustainable, environmentally friendly, economical practice, and releasing fewer additives (Alhazzawi, 2016; Aretxabaleta et al, 2021; Carneiro Pereira et al., 2021; de Oliveira Limírio et al., 2021; Mourouzis et al., 2020, 2022; Wei et al., 2022). In particular, 3D printing is more environmentally friendly than milling because it does not use discs, which are more costly and complex to reuse.

The main problem when studying the presence of additives released by dental materials in the organism is the extraordinary difficulty in associating them explicitly to this type of device, given that they are commonly found in our surroundings. Their multiple origins: environmental, nutritional, hygienic sources, etc., make it extremely difficult to associate the origin with the substance identified. For this reason, in vitro studies are a widely used method. However, the protocols developed to date show a certain lack of uniformity: in some, discs are analysed without considering the inhibited layer, in others their polishing does not correspond to the clinical protocol, or there is a lack of uniform extraction ratio, or the solvents are different, or salivary turnover is not taken into account (the possible alterations in its composition, pH, viscosity, or flow that may occur in the same subject, and its role in the chemical erosion of the material). On the other hand, in some of these tests, occlusal wear is not considered. They provide data on quantification and identification of the substances in saliva, mainly bisphenols, substitutes for

and phthalates, in different materials, depending on their manufacturing technique (milled, printed, injected), and their curing (thermo-, self-, photopolymerised). Clinical studies focus on paired samples, or on epidemiological, retrospective descriptive, comparative, retrospective and prospective studies where saliva, blood and urine samples are analysed to determine their assimilation. Among the methodologies used, the FDA (Food and Drug Administration) recommends High Performance Liquid Chromatography (HPLC) or Gas Chromatography (GC). Authors such as Hampe Tristan, advise Mass Spectrometry (MS), or the HPLC/MS tandem, establishing as ideal the combination of High Resolution Mass Spectrometry (HRMS) and MS, since it does not detect products such as Bis GMA, -EMA and -UDMA (De Angelis et al., 2022; Hampe et al., 2022; Kessler et al., 2020; Tichy et al., 2021). (Francisco et al., 2022; Van Landuyt et al., 2011a, 2011b; Vervliet et al., 2022; Wedekind et al., 2021).

The literature reports values within the limits ($4\mu\text{g}/\text{kg}/\text{day}$); however, some studies report higher concentrations in groups with associated pathologies than in those without. This is the case of the study carried out with patients with squamous cell carcinoma vs. control group, the results showed higher concentrations of BPA and phthalate metabolites (Hu et al., 2021; Wei et al., 2022; Zheng et al., 2017).

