1.4 OBJECTIVES

There is no evidence of release of substances of particular concern, or endocrine disruptors released from Michigan type acrylic occlusal splints.

General objectives: To describe and quantify the values of substances of very high concern (SVHC) or endocrine disruptors (ED) released from printed or injected acrylic Michigan type splints.

Specific objectives:

1. To identify the SEPs and EDs released by Michigan-type splints made by injection or *in vitro* impression technique, simulating oral environment and wear.
2. Identify SEPs and EDs in saliva released from printed or saliva-injected acrylic Michigan type splints before, during and after insertion in the mouth.
3. To quantify the levels of SEP and ED in saliva released from printed or injected acrylic Michigan type splints in saliva before, during and after insertion in the mouth.
4. Contrast the results obtained in the laboratory test with those recorded in the saliva samples of the *in vivo* study.

5. Relate the results to the manufacturing process, stage of exposure, time, habits and individual characteristics of each volunteer.

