2 METHODOLOGY OF THE STUDY

2.1 DESIGN

This is a prospective analytical observational experimental pilot study that aims to analyse the substances of particular concern and endocrine disruptors detected in saliva, released by conventional dental devices, before and after the intervention. They will therefore be paired samples, where the control group will be the same subject, minimising the independent variables: saliva pH, microbiome, salivary flow, habits, occlusal wear, erosion by external agents and saliva.

Saliva sampling shall be carried out in accordance with the conventional protocol RD 1716/2011. The saliva containers shall comply with the requirements of the ISO 6717:2021 standard. They shall be packaged and transported according to the protocol Order JUS/1291/2010 of 13 May. All samples shall be identified with the number assigned to the volunteer, time, material and type of manufacture (processed, machined or printed), and shall be sent to the Chemical Institute for Energy and Environment (IQUEMA). University of Cordoba, where they will be analysed by the SAC group, for subsequent statistical treatment and interpretation.

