2.5 PERIOD OF STUDY

Recruitment is expected to be completed in January 2024, and sample collection is expected to be completed in September 2024.

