2.6 DESCRIPTION OF THE STUDY

2.6.1 VOLUNTEER RECRUITMENT:

The study groups will be formed in accordance with the requirements and inclusion criteria. Each of the subjects will be informed of the purpose and methodology of the project by means of an information document for the volunteer (Appendix II) and must sign the informed consent form provided for this purpose (Appendix III); they may withdraw from participation at any time. The data of the participants will be stored in a clinical history with an individual key number, in accordance with the regulations contained in the current Organic Law 3/2018, of 5 December, on the Protection of Personal Data.

Appointments will be made as follows:

APPOINTMENT 1: A conventional computerised clinical history is taken of the patient, in which data is collected on general health, orofacial and nutritional habits and hygiene. We explain in detail what the treatment consists of: Michigan type relaxation splint (device to prevent tooth wear due to bruxism). Each intervention is governed by scientific and deontological criteria, respecting all the ethical rules of research. The following is a detailed description of the study, its duration and methodology. The four moments of saliva collection will be explained: before, during, and 3 and 6 months after placement, as follows:

-Time 0: the day of the appointment, before the intervention.

-Step 1: On the day of the appointment, device placement.

-Time 2: 3 months after device placement.

-Time 3: 6 months after treatment.

Information and informed consent will be provided.

APPOINTMENT 2: Preparation and taking of models for the Michigan type splint according to the conventional protocol for this treatment.

APPOINTMENT 3: The models will be assembled in the articulator to send and request the making of the splint, specifying whether it is injected or printed.

APPOINTMENT 4: A saliva sample is taken in the device for this purpose. After checking for proper fit and retention, the occlusal adjustments will be made with a handpiece and conventional acrylic and polishing burs. After completion of the procedure, a new saliva sample shall be taken. The samples shall be identified with the patient's assigned code and stored according to conventional standards. An appointment will be made after 6 months to continue with the study and in accordance with the check-up times for correct oral health.

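### Change from Time 0 at the follow-up visits is read as splint release, yet outside exposure to the same substances is neither standardised nor recorded when saliva is taken

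*Protocol*

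**What the plan says.** Section 1.2 of the protocol presents attribution to the device as the main difficulty in this field: "Their multiple origins: environmental, nutritional, hygienic sources, etc., make it extremely difficult to associate the origin with the substance identified". It gives this as the reason why laboratory studies are common.

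Section 2.1 sets the in vivo control: "They will therefore be paired samples, where the control group will be the same subject, minimising the independent variables". Habits are on the list that follows. Objective 3 in section 1.4 treats the saliva levels as release from the device: "To quantify the levels of SEP and ED in saliva released from printed or injected acrylic Michigan type splints in saliva before, during and after".

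Section 2.6.1 lists four samples. The only one without a splint is "Time 0: the day of the appointment, before the intervention". Time 1 is taken at the same visit, after the splint has been fitted and adjusted with burs. The others are "Time 2: 3 months after device placement" and Time 3 at 6 months. Both groups of 15 receive a splint (section 2.4).

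At Appointment 1, "data is collected on general health, orofacial and nutritional habits and hygiene". Appointments 5 and 6 comprise an oral and splint check and a saliva sample. The independent variables listed in section 2.6 are residence, manufacture, time, age and polymerisation. The Annex IV variables form has one column per volunteer and no entry for diet or hygiene products. Objective 5 and the end of section 2.6 nevertheless plan to relate the results to participants' habits.

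**The concern.** A person's own earlier value is a good control for whatever does not change in that person. Food, drink and oral-care products used shortly before a visit do change, and section 1.2 names these kinds of source as the obstacle. At the follow-up visits there is no fresh splint-free value from the same person and no splint-free group to show how background moves. Exposure that was not recorded on the day cannot be recovered by later analysis.

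At stake is the claim in objectives 2 and 3 that substances found in saliva during follow-up were released by the splint. If the study is run as written, a rise from Time 0 in a widespread substance could be release, recent outside exposure, or both.

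**Working it through.** **Is there a figure to reproduce?** No. The protocol gives no effect size, variability or power for these comparisons. Only the total checks: 2 × 15 = 30. The first part is therefore a comparison of the text.

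**What pairing removes.** Write a volunteer's later sample minus Time 0 as

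change = splint release + (background at the later sample − background at Time 0).

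The person's constant level cancels. The bracket does not.

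- *Time 1 − Time 0:* same visit, so the bracket should be small. Time 1 follows bur adjustment, however, so it does not represent release in use.
- *Times 2 and 3 − Time 0:* months apart, so the bracket is open. These are 30 × 2 = 60 of 30 × 4 = 120 planned samples. That is a count of exposed samples, not a measure of bias.
- *Printed versus injected:* both groups are followed, so drift common to both largely cancels.

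**What could control or explain the bracket.**

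| Possible safeguard | What the protocol provides |
|---|---|
| Conditions before sampling | None in the text shown. The decree cited in 2.1 for sampling is cited in 2.7.2 for ethical and legal requirements. |
| Exposure record per sample | None at Appointments 4 to 6 |
| Diet and hygiene history | Once, at Appointment 1; no Annex IV field |
| Splint-free group | None |
| In vitro screen (2.6, objective 4) | Yes: identifies what the material can release |

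The screen narrows the list of substances. It cannot divide a saliva concentration between splint and other sources.

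**Noise and bias are different.** Recent exposure that is as likely before Time 0 as before a later sample widens the spread of the changes without shifting their mean. Only a shift shared across volunteers biases the mean change.

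**Illustration of bias (assumed inputs).** Take zero release and a two-sided paired t-test at 0.05. Section 2.8 names Student's t-test without saying whether it is paired, so the paired form is an assumption. With a mean background shift of d standard deviations of the within-person difference, the test statistic is noncentral t with n − 1 degrees of freedom and noncentrality d√n. The probability of p ≤ 0.05 is:

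| d | n = 15 | n = 30 |
|---|---|---|
| 0 | 0.05 | 0.05 |
| 0.2 | 0.11 | 0.19 |
| 0.5 | 0.44 | 0.75 |
| 0.8 | 0.82 | 0.99 |

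On the log scale, with within-person SD s and a background ratio r, d = ln(r)/(s√2). For r = 1.5:

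- s = 0.5: d = 0.405/0.707 = 0.57; probability 0.54 (n = 15) or 0.86 (n = 30).
- s = 1.2: d = 0.405/1.697 = 0.24; probability 0.14 or 0.24.

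**Illustration of noise (assumed inputs).** With no shared shift and no release, the chance that one person at least doubles over a single baseline is 1 − Φ(ln 2/(s√2)). This is 0.16 for s = 0.5 and 0.34 for s = 1.2, or about 5 to 10 of 30 volunteers. The group test keeps its 0.05 level, but individual rises cannot be read as release.

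**Visit timing.** The list in 2.6.1 puts the follow-up samples at 3 and 6 months. The appointment text sets the next visit 6 months after Appointment 4 and the one after that 3 months later, which gives 6 and 6 + 3 = 9 months. The two do not agree, so the interval over which background can change is itself unsettled.

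**The case against.** The strongest reply is that the protocol does not rely on pairing alone. Section 1.2 points to laboratory work, section 1.3 rests the study on contrasting laboratory and saliva results, and the splint was chosen partly because it needs no extra plastic materials such as cements. The material is screened before any saliva is analysed. This stands, and it means the gap is partial. It leaves open how much of a widespread substance in later saliva came from the splint.

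It can also be said that habits are collected and are to be correlated with the results. So it would be wrong to infer that they are never recorded. A single history can serve comparisons between people, but it cannot explain change within a person.

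The volunteer information document and the in vivo timeline figure are not shown and might contain sampling instructions. The supportable statement is that the visible text gives none.

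A reader might infer a seasonal bias running the same way for most volunteers. The protocol does not support that. Section 2.5 says "Recruitment is expected to be completed in January 2024, and sample collection is expected to be completed in September 2024" but gives no start of recruitment, nothing is said about seasonal variation, and the visit intervals conflict. Nor does the protocol support any particular percentage of apparent release.

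Pilot status does not remove the point: section 1.3 says the pilot is meant to lay the groundwork for a protocol, and sampling conditions belong to that.

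**Conclusion.** The point holds in limited form. For the samples after placement day, the within-person change from Time 0 mixes splint release with changing outside exposure. The protocol names that exposure as the main obstacle, but in the text shown it neither standardises nor records it at sampling. Uncontrolled recent exposure adds noise, and any shared drift would bias the mean change. The documents give the size of neither; the probabilities above rest entirely on assumed shifts and variability.

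It would go too far to conclude that the study cannot attribute anything. The same-visit contrast is the least exposed to background, although it reflects a freshly adjusted splint. The printed-versus-injected contrast is less exposed if drift is similar in both groups. The laboratory screen limits which substances can be candidates. This is a worthwhile correction to make before sampling, not a fatal flaw.

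**What to change.** 1. In 2.6.1, set identical pre-sampling conditions for all four samples: the same time of day, and a fixed interval without food, drink, chewing gum, tooth-cleaning or mouthwash. In Annex IV, record compliance and recent exposure for each sample, and add the habit fields that objective 5 needs.
2. For samples after placement day, report widespread substances as detected in saliva. Claim release only for substances that the same material also released in vitro and that are raised over the person's own Time 0, with the background caveat stated. Describe Time 1 minus Time 0 as the contrast least exposed to background, and say that it follows bur adjustment and does not represent release in use.
3. Reconcile the sampling times listed in 2.6.1 with the intervals in the appointment text.

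Suspect-list substances that the material did not release in vitro could serve as an exploratory check on drift, but no more. The plan is to quantify prioritised compounds identified in the laboratory stage, so no quantification of the others is foreseen, and they need not share sources with the splint substances.

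The cost is a short instruction to volunteers, a few form fields and a weaker claim at the later times. No extra visits or volunteers are needed.
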